### 3.4 **Pharmaceutical Data**

*Absorption and Distribution:* Following a single oral dose of 20 mg tamoxifen (standard-dose tamoxifen), an average peak plasma concentration of 40 ng/mL (range 35 to 45 ng/mL) occurred approximately 5 hours after dosing. The decline in plasma concentrations of tamoxifen is biphasic with a terminal elimination half-life of about 5 to 7 days. The average peak plasma concentration of N-desmethyl-tamoxifen is 15 ng/mL (range 10 to 20 ng/mL). The average steady-state plasma concentrations of tamoxifen and N-desmethyl-tamoxifen after administration of 20 mg tamoxifen once daily for 3 months are 122 ng/mL (range 71-183 ng/mL) and 353 ng/mL (range 152-706 ng/mL), respectively. Chronic administration of 10 mg tamoxifen given twice daily for 3 months to patients results in average steady-state plasma concentrations of 120 ng/mL (range 67-183 ng/mL) for tamoxifen and 336 ng/mL (range 148-654 ng/mL) for N-desmethyl tamoxifen. After initiation of therapy, steady state concentrations for tamoxifen are achieved in about 4 weeks and steady-state concentrations for N-desmethyl tamoxifen are achieved in about 8 weeks, suggesting a half-life of approximately 14 days for this metabolite. In a steady-state, crossover study of 10 mg tamoxifen tablets given twice a day vs. a 20 mg tamoxifen tablet given once daily, the two schedules were found to be bioequivalent.

*Metabolism:* Tamoxifen is extensively metabolized after oral administration. N-desmethyl tamoxifen is the major metabolite found in patients' plasma. The biological activity of N-desmethyl tamoxifen appears to be similar to that of tamoxifen. 4-Hydroxytamoxifen and a side chain primary alcohol derivative of tamoxifen have been identified as minor metabolites in plasma. Tamoxifen is a substrate of cytochrome P-450 3A, 2C9 and 2D6, and an inhibitor of P-glycoprotein.

*Excretion:* Studies in women receiving 20 mg of C-tamoxifen have shown that approximately 65% of the administered dose was excreted from the body over a period of 2 weeks with fecal excretion as the primary route of elimination. The drug is excreted mainly as polar conjugates, with unchanged drug and unconjugated metabolites accounting for less than 30% of the total fecal radioactivity.

*Pregnancy: Category D.* Tamoxifen may cause fetal harm when administered to a pregnant woman. Women should be advised not to become pregnant while taking tamoxifen or within 2 months of discontinuing tamoxifen and should use barrier or other

nonhormonal contraceptive measures if sexually active. Tamoxifen does not cause infertility, even in the presence of menstrual irregularity.

### 3.5 **Supplier**

Tamoxifen is commercially available in 10 mg and 20 mg tablets. For this trial, generic 5mg capsules and matching placebo capsules will be manufactured by Sharp Clinical Services.

Tamoxifen and matching placebo will be manufactured as a capsule for oral administration. Each 5 mg tamoxifen capsule contains 7.6 mg of tamoxifen citrate, which is equivalent to 5 mg of tamoxifen, as well as anhydrous lactose, colloidal silicon dioxide, crospovidone, magnesium stearate, microcrystalline cellulose and sodium lauryl sulfate, as inert excipients. Matching placebo capsules will contain anhydrous lactose.

For this study, blistered cards will contain a month's supply of tamoxifen 5mg or matching placebo capsules.

### 3.6 **Storage and Stability**

Tamoxifen 5 mg capsules and matching placebo will be shipped at room temperature. The capsules should be stored at a controlled room temperature of 20-25°C (68-77°F) in the supply kits containing the blister cards. They will be stored and dispensed in the original containers.

### 3.7 **Administration**

Trial participants will be instructed to take one capsule per day orally. They will be instructed to swallow the capsule whole, with water or another non-alcoholic liquid, preferably the same time each day. They may take the capsules with or without food. If they forget a dose, participants will be asked to take it when they remember, and then take the next dose as usual, but if they do not remember until their next dose, to not take extra capsules to make up the missed dose.

For premenopausal subjects, they will be instructed to begin their study medication course while menstruating or after negative beta-HCG test as below. For premenopausal subjects who do not have regular menstrual periods or are between periods, a beta-HCG level will be performed to confirm that the patient is not pregnant before starting study medication. Participants will be warned that they should avoid pregnancy while taking study medication and for two months after discontinuation. They will be advised to use barrier or nonhormonal contraceptive measures.

## 4.0 **RECRUITMENT STRATEGY**

Via the Consortium for Pediatric Interventional Research (CPIR), a consortium of five institutions, including the *City of Hope National Medical Center (COH)*, *St. Jude Children's Research Hospital (SJCRH)*, *Emory University (EU)*, *University of Michigan (UM)*, and *Princess Margaret Hospital in Toronto (PMH)*, we have constructed a cohort of HL survivors who were exposed to chest RT during childhood or young adulthood, at least 5 years prior to study participation. This cohort will form the initial basis from which accrual in this trial will be conducted. Other sites and additional CAYAC diagnoses treated with RT involving the chest may be added as needed to complete accrual for the trial.

Recruitment will be conducted both prospectively and retrospectively as described below. Because this is a highly motivated patient population, at study activation we anticipated that it would be feasible to achieve a recruitment yield of 30%, and that the accrual goal of 230 would be achievable across the CPIR participating institutions described above. After the initial two years of accrual, we observed an average recruitment yield of only 14%. Therefore, new sites were recruited, and additional sites have been identified and will be recruited as needed to reach the accrual goal.

#### 4.1 **Retrospective recruitment**

Participants in any long-term cancer survivorship clinic, database or registry associated with a participating site, who are alive and eligible based on medical record review will be mailed a letter and study brochure describing the study. The letter lets them know that a representative from the study will be calling to tell them more about the study, unless they opt out (i.e. passive consent). Upon contact, the patient will be given another opportunity to opt out. Patients who agree to be prescreened will be interviewed per the [Intake Form](#). Subjects who are screened by this method will form *cohort 1*.

#### 4.2 **Prospective recruitment**

Alternatively, the study will be introduced to eligible patients at their survivorship and/or high risk screening and/or prevention clinic visit and given a brochure describing the study to take home to read. The study clinical research associate (CRA) or clinical research nurse (CRN) will then follow up with a call the following week to assess interest and confirm eligibility. Subjects who are screened by this method will form *cohort 2*. Patients may also self-identify and call in to a local site via recruitment advertising on the internet or from a flyer placed in the community (such as community centers, libraries and churches). Self-identifying subjects will form *cohort 3*.

#### 4.3 **Informed consent process**

Eligible and interested individuals will be approached for informed consent. One of the members of the Protocol Management Team (PMT) at each site will introduce the study to potentially eligible patients, either at a survivorship clinic visit or via a mailing as described. The PMT at each site includes the consortium PI, the co-investigator, and the clinical research nurse (CRN), and/or clinical research associate (CRA). All potential risks and benefits of the study, as well as alternatives, will be fully explained. Whenever possible, the informed consent process will be conducted in the patient's preferred language. If that is not possible, a professional translator will be used.

## 5.0 ELIGIBILITY CRITERIA

### 5.1 **Inclusion Criteria**

The following are requirements for entry onto this Phase IIb trial:

- Females, 25 years of age or older at the time of registration
- Exposure to RT delivered to the chest, axilla, and/or supraclavicular areas at a cumulative dose of 12 Gy or more by age 40 years. In addition, patients who received total body irradiation by age 40 may be considered.

- No evidence of active disease from their primary cancer for at least 2 continuous years prior to registration. The indication for RT is not specified but cannot be for primary breast cancer. Common examples of primary cancer diagnoses include, but are not limited to: lymphoma, leukemia, sarcoma, and Wilms tumor occurring in pediatric patients, and lymphoma, leukemia, and sarcoma occurring in young adults. Primary cancer therapy must have been completed at least 6 months prior to registration.
- Well-defined menopausal status falling into one of the following categories:
  - Premenopausal, defined as age at registration 45 years old or younger with regular monthly period for at least 6 consecutive months prior to registration.
  - Postmenopausal, defined as continuous absence of menstruation for 12 months *OR* status-post bilateral oophorectomy *OR* follicle stimulating hormone (FSH) level in the postmenopausal range.

[figure not shown]
## 5.2 Exclusion Criteria

Subjects will be excluded if any of the following characteristics are present:

- SMN other than those listed below diagnosed within 2 years of study entry. Patients with the listed indolent or pre-invasive neoplasms may be eligible if diagnosed within 2 years and all treatment was completed at least 6 months prior to registration:
  - non-melanoma cancers of the skin
  - thyroid cancer
  - cervical cancer confined to the cervix or cervical intraepithelial neoplasia (CIN)
  - ductal carcinoma in situ (DCIS) or breast IEN (includes atypical hyperplasia and LCIS)
  - superficial or non-invasive transitional cell carcinoma of the bladder

For women with a prior history of ductal carcinoma in situ (DCIS) or breast IEN, only one breast could have been involved and all therapy must have been completed at least 6 months prior to registration. In addition women with a prior history of invasive breast cancer may also be eligible, as long as only one breast was involved, they were diagnosed at least 2 years prior to study entry, and therapy was completed at least 6 months prior to study entry.

- Bilateral breast implants or status-post bilateral prophylactic mastectomy.
- Evidence of malignant breast disease on any form of breast imaging. The study only requires annual mammography; however, annual breast MRI is considered standard of care in this patient population (per COG or NCCN follow-up guidelines), and breast ultrasound may be indicated if a palpable lesion is detected on screening clinical breast exam. Abnormal imaging may require additional radiographs and/or breast biopsy. Patients who are found to have benign breast disease with or without atypia may continue on study as long as there is no evidence of malignancy. If there is evidence of malignancy, and only one breast is involved, they may be reapproached 6 months after completion of therapy for consideration of the trial.
- Baseline categorical mammographic density scored as BIRAD 1, or extremely fatty, in both breasts (see Figure 9). If the patient has a prior history of IEN (DCIS, LCIS, or atypical hyperplasia), the contralateral breast must not have a mammographic density score of BIRAD 1. This determination will be made at the local site.

- Current or recent use (within 6 months of registration or baseline mammogram, whichever is first) of any of the following hormonal agents:
  - systemic hormone replacement therapy (includes oral or transdermal formulations). Vagifem and Estring, two formulations of locally applied vaginal estrogen associated with minimal systemic absorption, may be allowed. Other estrogen-containing vaginal creams, while not an exclusion, should be avoided whenever possible. Patients with a history of hormone modifying herbal supplements (see section 11.14) are eligible, but patients will be asked to avoid their use after on study.
  - hormonal forms of contraception (includes oral, transdermal, implanted, and injectable formulations),
  - selective estrogen receptor modifiers (such as tamoxifen and raloxifene),
  - aromatase inhibitors,
  - GnRH analogs,
  - prolactin inhibitors, or
  - androgens or antiandrogens.
- Concurrent use of warfarin and strong inhibitors of CYP2D6 (see Section 11.15 for a list) will not be allowed.
- A personal history or a strong family history of venous thromboembolism, (VTE), including deep venous thrombosis (DVT) or pulmonary embolus (PE). A one-time personal history of catheter-associated DVT may be allowed, as long as there were no subsequent VTE events and a strong family history is not present. Examples of a strong family history include (but are not limited to): one first degree relative with more than one VTE event in the same individual, and two family members in the same lineage with unexplained VTE or two VTE events in the same individual. If a family history is present, but it is not clear whether or not it is clinically significant, consideration of genetic testing to rule out a hereditary clotting syndrome (e.g. FVL, prothrombin G2010A mutations) may be considered. Because of a drug-drug interaction with tamoxifen, concurrent with warfarin use for any reason is not allowed.

For this reason, patients with atrial fibrillation may not participate. However, patients with coronary artery disease or congestive heart failure without atrial fibrillation may be allowed to participate. Patients with a personal history of a cerebrovascular accident (CVA), transient ischemic attack (TIA), or retinal vein thrombosis will not be allowed to participate.

- Current intrauterine pregnancy or plans to become pregnant within two years. In addition, currently nursing mothers will be excluded.
- Renal or hepatic insufficiency, defined as having a serum creatinine, total bilirubin, SGOT, or SGPT greater than 2x the institutional norm.
- Unable to provide consent.

## 6.0 DOSE SCHEDULE AND RULES FOR TREATMENT DISCONTINUATION

### 6.1 Dose Schedule

Randomization will be stratified according to the rules outlined in Section 12.3. Subjects will be randomized 1:1 to receive low-dose tamoxifen 5 mg or placebo daily for 24 months. Registration will be done via a central database, Interactive Web Response System (IWRS), which will also perform stratified treatment assignment. This system is maintained by Sharp Clinical Services, which is separate from the coordinating center and all participating sites such that all study staff (except for the statistician when preparing reports for the DSMB) will remain blinded.

### 6.2 Dose Escalation

There will be no dose escalation in this Phase IIb study.

### 6.3 Criteria for Discontinuation of Study Protocol Therapy

- Patient requests to withdraw from study
- Treatment interruption longer than 90 consecutive days
- A breast or gynecologic event (see definitions below)
- Pregnancy
- The occurrence of a grade 2 toxicity with *probable* or greater attribution without resolution within 72 hours, or any grade 3 or 4 toxicity with *possible* or greater attribution meeting definitions below
- Death

A *breast event* is defined as a new diagnosis of DCIS or invasive BC. These events are expected to occur as a consequence of the high risk study population. In the case that it should occur, the subject will be taken off study and referred to the appropriate breast surgeons and medical oncologists for proper diagnostic work-up and treatment. For subjects who develop atypical hyperplasia (AH) or lobular carcinoma in-situ (LCIS), or any other form of benign breast disease, their specific histologic diagnosis and the date of diagnosis will be recorded, but they may continue on study.

A *gynecologic event* is defined as a new diagnosis of endometrial carcinoma or uterine sarcoma. Although these events may occur sporadically, they have been associated with standard dose tamoxifen and therefore are listed among criteria for discontinuation of study treatment. In the case that a subject should experience dysfunctional uterine

bleeding of any etiology, the subject will be referred to a gynecologist for proper diagnostic work-up. Should such a work-up lead to a diagnosis of endometrial carcinoma or uterine sarcoma, the subject will be taken off study and referred to a gynecologic oncologist for appropriate treatment. Otherwise, their specific histologic diagnosis and the date of diagnosis will be recorded, but they may continue on study.

Participants must not be planning to become pregnant for two years to be eligible for the study, and they will be warned about the importance of not becoming pregnant while on study at the time of enrollment. They will be advised to use either a barrier method or another nonhormonal form of contraception (eg. hormone-free IUD) for all sexual activity during the course of the study. Nevertheless, occurrence of an unplanned intrauterine pregnancy while on study will be an indication for immediately stopping treatment and the patient must withdraw from the study. If the patient should become pregnant while on study, or within two months after discontinuing therapy, her treatment assignment will be unblinded immediately. If the patient was randomized to tamoxifen, then they must be apprised of the potential risk of spontaneous abortion, birth defects, or a DES-like syndrome.

The Principal Investigator (PI) at each site is responsible for monitoring protocol conduct and reporting to their Institutional Review Board (IRB) any adverse events (AEs) related to either the study medication per their institutional guidelines. AEs must also be reported to the Coordinating Center (UAB) per instructions in Section 8.0. The NCI common toxicity criteria for adverse events Version 4.0 (CTCAE v.4.0, Publish Date 10/19/2009) will be used to assess toxicity.

With the exception of vasomotor and gynecologic symptoms commonly associated with menopause, all grade 2 or greater toxicities of clinical significance with *possible* or greater attribution (please refer to Section 8.3 for definition) to the study drug will be reviewed by the Protocol Management Team (PMT) at the local site. The PMT includes the consortium PI, the consortium co-investigator, and the CRA/CRN.

- Any grade 2 toxicity besides vasomotor and/or gynecologic symptoms commonly associated with menopause with *probable* or greater attribution to the study drug will be brought to the attention of the local PI (within 24 hours of knowledge of the event) for close monitoring. If the symptom resolves or improves within 72 hours, the patient may continue on the study medication. Otherwise, the patient will be unblinded and taken off therapy.
- A patient reporting grade 3-4 toxicity with *possible* or greater attribution to the study drug will be unblinded and taken off protocol therapy.

Serious adverse events (SAE) and all grade 3-4 toxicities with *possible* or greater attribution to the study drug must be submitted to the coordinating center PI and study staff immediately (within 24 hours of knowledge of the event), to allow reporting to the local and central IRBs and the central DSMB. If a Grade 3-4 AE is determined to have *possible* attribution to low-dose tamoxifen, an AE report will be submitted to the Food and Drug Administration (FDA) as described in Section 8.0.

Because venous thromboembolic events have been associated with standard dose tamoxifen, we include CTCAE specific to DVT, PE, and stroke below.

**CATEGORY:** VASCULAR

**Adverse Event:** Thrombosis/embolism (vascular access-related)

**MedDRA Code:** 10062169

Grade	Description
1	Venous thrombosis (e.g., superficial thrombosis)
2	Venous thrombosis (e.g., uncomplicated deep vein thrombosis), medical intervention indicated
3	Thrombosis (e.g., uncomplicated pulmonary embolism [venous], non-embolic cardiac mural [arterial] thrombus), medical intervention indicated
4	Life-threatening (e.g., pulmonary embolism, cerebrovascular event, arterial insufficiency); hemodynamic or neurologic instability; urgent intervention indicated
5	Death

The following are considered clear indications for discontinuation of study protocol therapy (confirmed by clinical diagnosis):

- Deep venous thrombosis (DVT)
- Pulmonary embolism (PE)
- Transient ischemic attack (TIA)
- Cerebral vascular accident (CVA)
- Retinal vein thrombosis
- Cardiac ischemia/infarction

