In summary, because the dose that we will be administering will be 5 mg per day rather than 20 mg per day, we expect no significant increase in these adverse events in the treatment group compared to the placebo group. In addition, the median age of the patient cohort from which trial participants will be drawn is 36 years old, while the adverse effects associated with the 20 mg per day of tamoxifen were only significantly elevated above placebo among women who were 50 years old or older at the time of treatment initiation. However, precautions will be taken, nevertheless (see Section 8.2 for guidelines regarding adverse event reporting and for data safety monitoring). In addition, women with childbearing potential will be warned that they should avoid pregnancy while taking study medication and for two months after discontinuation.

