The final study visit will be conducted on **Day 730**, during which a final history and physical (reported on the **General History and Physical Form**), fasting blood draw, and urine collection will be performed. For patients who completed a baseline RPFNA, a post-treatment RPFNA will also be performed. Adherence will be reported on the **Adherence Tracking Form**, and patient-reported symptoms will be assessed via **Symptom Log**. Patient reported health status changes will be assessed using the **Health Assessment Form**. All lab results will be reported using a **Lab Values Form**. A repeat mammogram using a digital mammography machine with large paddles and

timed to the follicular phase of the menstrual cycle (Days 2-10) will also be performed. The patient will be encouraged to have their mammogram at the same facility that did the initial study mammogram. If annual screening breast MRI is indicated (per COG or NCCN follow-up guidelines), a repeat breast MRI should also be performed. If done while on study, it is suggested to time it to the follicular phase of the menstrual cycle (Days 2-10). A final telephone follow-up will occur one week later (**Day 738**) to ensure that the post-treatment RPFNA was well tolerated (only for patients consenting to the RPFNA procedure before protocol version 3/9/2015 and all previously consented patients as of 10/26/15).

All forms are due within 28 days of each scheduled visit and should be entered on the study Electronic Data Capture (EDC) website. Please refer to the [Treatment Monitoring and Follow-up SOP](#) for detailed instructions.

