#### 9.5 **Long-term Follow-up**

After trial completion, the patient should be referred back to their local long-term survivorship clinic for continued follow-up, with their first return visit scheduled one year after their Day 730 study visit. Their first return visit will represent a new baseline survivorship clinic visit, and all organ function baseline assessments included in the COG survivorship guidelines should be repeated. This includes a comprehensive metabolic panel, which is recommended to be performed at baseline and as needed. Because of the association between standard dose tamoxifen and hepatic disease, special attention should be paid to symptoms and signs of hepatic disease on all subsequent annual follow-up survivorship clinic visits.

To monitor for significant medical events, including second malignancies that may occur after the two-year intervention, sites will submit an [Annual Follow-Up Form](#) for up to 10 years post-study completion, including participants that complete the two-year intervention and those that withdrew prior to completion. Subjects who are lost to follow-up will be reported to the coordinating center using this form. New cancer and any inpatient or outpatient procedures potentially related to the study will be reported using the [Breast Event Form](#) and [Other Event Form](#).

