#### C. Molecular characteristics.

The following variables are known to influence efficacy of tamoxifen in the treatment of BC patients and will be analyzed at a later date.

*Endoxifen levels* – continuous, time-varying. These data will be available at t1 and t2.

*CYP variants* - dichotomous (yes/no), constant over the study period.

In addition to testing their significance as effect modifiers, we will also examine their relationship with the outcome variables (MBD, cytomorphology, proliferative index, etc) to validate known relationships. Proc Mixed for normal data and Proc GLMMIX for non-normal data in SAS 9.1 (Cary, North Carolina) will be used for analysis.

***Exploratory Aim 2: To examine the relationship between a low-dose tamoxifen regimen and clinical measures of efficacy and toxicity.***

For measures of clinical efficacy, we will document the occurrence of new breast cancer and DCIS diagnoses.

The assessment of clinical toxicity will include the following outcomes/measures:

- 1) incidence of uterine and other cancers during the study;
- 2) gynecological symptoms: any and the frequency of hot flashes, night sweats, vaginal discharge, vaginal bleeding or spotting, missed menstrual periods for pre-menopausal women, genital itching/irritation, and pain with intercourse, to be obtained from symptom log administered 10 times (baseline, days 28, 90, 180, 270, 365, 455, 540, 630, 730) ;
- 3) incident thromboembolic events (DVT, PE, TIA or stroke, and retinal vein thromboses);

4) incidence of cataract;

5) liver function abnormalities: total bilirubin, SGOT/AST, SGPT/ALT, measured at baseline, year 1, and year 2.

The *incidence* of new breast cancer, DCIS, non-breast malignancies, thromboembolic events, and cataract are expected to be low ( $\leq 5$  events per arm) during the study period given the sample size, based on statistics quoted in Investigational Brochure. Thus, we will initially compare the frequency of events by treatment group in a 2x2 table using the Fisher exact test, stratified on CYP2D6 status. We will also use poisson regression in cohort analysis to examine treatment differences in these outcomes adjusted for covariates, including CYP2D6.

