#### Annual Follow-up Form:

To monitor for significant medical events, including second malignancies that may occur after the two-year intervention, the CRA/CRN will submit an **Annual Follow-Up Form** for up to 10 years post-study completion, including for participants who withdrew prior to completing the study. Subjects who are lost to follow-up will be reported to the coordinating center using this form. New cancers and any inpatient or outpatient procedures potentially related to the study will be reported using the **Breast Event Form** and **Other Event Form**.

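### Pregnancy in the two months after the last capsule triggers immediate unblinding, but after Day 730 no visible scheduled contact asks about it for about a year, and the planning and contraception wording stops two months short

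*Combined protocol and SAP*

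**What the plan says.** Section 6.3 makes pregnancy a reason to stop treatment and withdraw. It extends unblinding beyond treatment: if pregnancy occurs on study or "within two months after discontinuing therapy, her treatment assignment will be unblinded immediately". It adds: "If the patient was randomized to tamoxifen, then they must be apprised of the potential risk" of miscarriage, birth defects or a DES-like syndrome.

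On study there is a route to detection. Under Section 12.4, Exploratory Aim 2, the Symptom Log covers "missed menstrual periods for pre-menopausal women" and is administered ten times, the last at Day 730. Beta-HCG appears in the Study Calendar at screening only, if needed.

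After Day 730, Section 9.4 has one further call: "A final telephone follow-up will occur one week later". It is limited to women who had RPFNA and checks tolerance of that procedure, which was discontinued for all participants on 10/26/15. Section 9.5 then refers women back to the survivorship clinic, "with their first return visit scheduled one year after their Day 730 study visit". Annual follow-up is described as monitoring significant medical events, including second malignancies. On event reporting, Section 14.3 says: "New cancers and any inpatient or outpatient procedures potentially related to the study will be reported using the" Breast Event Form and Other Event Form. Pregnancy is not named.

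Women are told about the window. Section 3.3 says that "women with childbearing potential will be warned that they should avoid pregnancy while taking study medication and for two months after discontinuation", and Sections 3.7 and 7.1 repeat this. The surrounding wording varies. Sections 3.4 and 3.7 set contraception advice beside the two-month window. Section 6.3 advises contraception "for all sexual activity during the course of the study", and 7.1 only for time on study. Sections 5.2 and 6.3 screen for plans to conceive within two years.

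**The concern.** The steps in 6.3 are time-critical and can begin only once the site knows of the pregnancy. In the window where the rule still applies but study visits have ended, nothing visible prompts the question. If a woman does not call in, the next scheduled contact can come after a term delivery, too late for counselling during the pregnancy. Section 8.2.2 makes a congenital abnormality a serious adverse event reportable within 24 hours, but a site unaware of the pregnancy may not learn of one.

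The wording points the same way. A woman who intends to conceive in month 25 meets the planning criterion as written. If she follows only the contraception advice in 6.3, she is unprotected during the two months that the protocol itself treats as at risk.

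**Working it through.** **Schedule after a last capsule at Day 730.** Two calendar months is at most 62 days.
- Window closes: 730 + 62 = Day 792.
- Next scheduled contact (9.5): 730 + 365 = Day 1095.
- Gap after the window closes: 1095 − 792 = 303 days.
- The RPFNA-only call at Day 738 covered 8 days of the window and asked about something else.

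**Timing against delivery.** Assume 266 days from conception to term; the documents give no figure.
- Conception on day 0 after the last capsule: delivery on day 266, which is 365 − 266 = 99 days before the annual visit.
- Conception on day 62: delivery on day 62 + 266 = 328, which is 365 − 328 = 37 days before it.

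This is conditional. The Study Calendar allows in-person visits 60 business days either side (12 weeks, 84 calendar days). If the final visit is late and the capsules have already ended, its Symptom Log can fall inside or after the window, and the gap shrinks or closes.

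**Wording.** Treatment is 24 months and the window 2, so the at-risk period is 24 + 2 = 26 months from first dose. The planning criterion covers 24. Contraception wording in 6.3 and 7.1 ends with the study.

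**Women and woman-years.** Section 12.5 assumes 67% premenopausal and 94 women per arm at the end of the study. That second figure is close to 115 × 0.9 × 0.9 = 93.2; I use the plan's 94.
- Premenopausal overall: 230 × 0.67 = 154.1.
- Completers: 2 × 94 = 188; 188 × 0.67 = 126.0; × 2/12 = 21.0 woman-years.
- Early leavers: 230 − 188 = 42; 42 × 0.67 = 28.1; × 2/12 = 4.7 woman-years. This is an upper bound, since some leave because of pregnancy or death and some cannot be reached.
- Total: 21.0 to 25.7 woman-years.
- For each 1 pregnancy per 100 woman-years: 0.210 to 0.257 pregnancies, half on tamoxifen, so 0.105 to 0.128.

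The documents give neither a pregnancy rate nor the share that would go unreported, so the number missed cannot be estimated.

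**Exposure within the window.** Section 3.4 gives half-lives of 5 to 7 days for tamoxifen and about 14 days for the main metabolite. Parent drug remaining is 0.5^(t/h). The metabolite is still being formed from residual parent. From steady state, with simple first-order kinetics, the fraction remaining is (kp·e^(−km·t) − km·e^(−kp·t)) / (kp − km), where kp = ln 2/5 or ln 2/7 and km = ln 2/14.

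| | Day 14 | Day 60 |
|---|---|---|
| Parent | 14% to 25% | under 0.3% |
| Metabolite | about 70% to 75% | about 8% to 10% |

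The earliest conceptions carry the most exposure, so prompt self-report matters more than any later call.

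**Timing of a back-up call.** Assume 14 days from last period to conception and 14 from conception to the missed period.
- A conception on day 62 gives a missed period on day 62 + 14 = 76, so a call at day 80 has a small margin.
- At day 80, a day-0 conception is at (80 + 14)/7 = 13.4 weeks by last period, and a day-62 conception at (18 + 14)/7 = 4.6 weeks.

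**The case against.** The case for leaving the plan alone has real weight. The sentence in 6.3 is conditional: it prescribes a response to a pregnancy and does not promise surveillance. Women are warned about the two months in three places and have had two years of contact with site staff, so relying on them to call is defensible. The SOPs, form fields and consent pages are not available here and may contain a pregnancy question or a number to call. Annual follow-up of significant medical events is not an exhaustive list. All of this stands, and it limits the finding to what the visible documents schedule.

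Three stronger readings are tempting and are not supported.
- A reader might infer a one-year gap for every woman, including those who leave early. The year is documented only after Day 730. No date is given for the first annual form after withdrawal, and a woman who stops capsules is withdrawn only after more than 90 consecutive days, so some windows pass while quarterly contacts continue.
- A reader might infer that women are not told about the window, or that 7.1 omits it. Section 7.1 carries the warning; only its contraception sentence is narrower.
- A reader might infer that women have no way to report. The contact number described in 9.3 is on the kit label, and kits are collected at Day 730, but that does not show that a woman lacks another number.

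The wording differences could be called editorial, since nothing tells a woman that conceiving in the window is acceptable. But the planning criterion still admits a woman whose stated plan falls inside it.

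**Conclusion.** The concern holds for women whose last capsule is at about Day 730: the visible plan leaves a mandatory, time-critical step dependent on self-report, with the next scheduled contact about a year after the final visit. For early leavers the size of the gap is not documented. The planning criterion in 5.2 and 6.3 and the contraception wording in 6.3 and 7.1 are two months shorter than the protocol's own risk window.

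The expected number of events is small, about 0.10 to 0.13 tamoxifen-exposed pregnancies per 1 per 100 woman-years, and not all would go unreported. The delivery timing assumes a 266-day gestation, a last capsule at the final visit and no self-report. A reader might infer some threat to the trial's results; there is none, because the primary endpoint, power and analysis plan are untouched. This is a cheap safety improvement of low severity. If an SOP or form already asks the question, a cross-reference would settle the detection part and only the wording would remain.

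**What to change.** 1. In 6.3 and 7.1, state that contraception applies while on study and for two months after the last capsule. For women still to be enrolled, extend the planning criterion in 5.2 and 6.3 to two years plus two months.
2. When the Study End Form is completed, which Section 14.3 requires for completers and withdrawals alike, repeat the two-month warning, give a contact number to keep, and tell the woman to call at once if she misses a period. This does most of the work for early conceptions.
3. Replace the obsolete Day 738 call with one call by the CRA or CRN about 80 days after the last capsule. Count from the capsule because visit dates can move by 60 business days. Call women of childbearing potential, asking about missed periods and pregnancy. Arrange beta-HCG if either is reported, and follow 6.3 if it is positive.

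The cost is a short amendment and at most about 154 brief calls by existing staff (about 126 completers and 28 early leavers). The final contact comes later than now. The call is a back-up: without self-report it finds the earliest conceptions only at about 13 weeks, and it may miss a late conception in a woman with irregular cycles. The analysis plan does not change.
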